## 8.2 MAD part

### 8.2.1 Steady-State

Steady-state will be assessed by visual inspection of the pre-dose concentrations on Days 4, 5, 6 and 7.

### 8.2.2 General Consideration

The PK parameters will be derived individually for each volunteer from drug concentrations in blood samples. Values below or above the limit of quantification, if any, will be indicated as such and will be taken into account for the calculation of pharmacokinetic parameters after confirming or correcting the relevant value. Blood samples will be taken according to the schedule given in [Table 2](#). (see [sec.10.2](#) below)

Actual blood sampling time points will be used for individual calculations and presentations. Nominal times will be used for calculations and presentations of summarised data.

Descriptive statistics will be calculated for PK parameters on Day 1 ( $AUC_{0-\tau}$ ,  $C_{max}$ ,  $t_{max}$ ), on Day 7 at steady-state ( $C_{max,ss}$ ,  $t_{max,ss}$ ,  $CL_{ss}/F$ ,  $V_{ss}/F$ ,  $Swing$ ,  $PTF\%$ ,  $C_{trough}$ ,  $C_{av}$ ,  $C_{min}$ ), and in addition  $AUC_{0-last}$ ,  $\lambda_z$ ,  $t_{1/2}$ , and  $AUC_{0-inf}$  using Phoenix WinNonlin 8.3. A non-compartmental model will be assumed for all parameters.

In cases where the  $\lambda_z$  rate is not assigned, the values of  $AUC_{0-inf}$  and  $t_{1/2}$  will not be estimated and will be reported as “Not calculated”.

Graphical images will be given as individual and overlaying (pooled) plots by treatment. Linear and semi-logarithmic views will be produced.

All plasma concentrations and derived PK parameters for each treatment will be listed and summarized descriptively (mean values (arithmetic and geometric), standard deviations, minimum and maximum values, medians, and valid Ns for the calculated variables). Coefficient of variation (CV%) of the arithmetic and geometric mean values will also be presented. 95% CI for arithmetic mean will be given where possible.

Accumulation ratios on the base of  $C_{max}$  and on AUC will be calculated.

### 8.2.3 Computation formulas (MAD)

Pharmacokinetic parameters will be calculated assuming a non-compartmental model as follows:

i) On Day 1 and at steady-state

- $AUC_{0-\tau}$  (h.ng/mL) – Area Under the Curve over a dosing interval, as calculated by the linear trapezoidal method:

$$AUC_{0-\tau} = AUC_{i-1} + \frac{C_i - C_{i-1}}{2} * (t_i - t_{i-1}),$$

where  $C_i$  is the value of observed plasma concentration at moment  $t_i$ .

- $C_{max,ss}$  (ng/mL) - Maximum plasma concentration at steady state.
- $t_{max,ss}$  (h) – Time until  $C_{max,ss}$  is reached.

- Swing(%) - The degree of fluctuation over one dosing interval at steady state:

$$Swing(\%) = \frac{C_{\max,ss} - C_{\min,ss}}{C_{\min,ss}} \times 100.$$

- PTF% - Peak to Trough Fluctuation within a complete dosing interval at steady state:

$$PTF(\%) = \frac{C_{\max,ss} - C_{\min,ss}}{C_{av}} \times 100.$$

- $CL_{ss}/F$  (L/h) – Apparent total body clearance following extravascular administration:

$$CL_{ss} / F = \frac{Dose}{AUC_{0-\tau}}.$$

- $V_{ss}/F$  - Apparent volume of distribution:

$$V_{ss} / F = \frac{CL_{ss} / F}{\lambda_z}, \text{ where } \lambda_z \text{ is terminal elimination rate constant estimated from corresponding single dose.}$$

- $C_{through}$  - Concentration reached immediately before the last dose is administered.

- $C_{av}$  - Average concentration over a dosing interval:  $C_{av} = \frac{AUC_{0-\tau}}{\tau}.$

- $C_{\min,ss}$  - Minimum observed concentration over a dosing interval.

ii) After Day 7: formulae are similar to those given in [sec. 8.1.2](#) for single dose.

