14 STATISTICAL METHODOLOGY AND ANALYSES

14.1 Statistical analysis plan

The study is exploratory and is not powered to address any pre-defined hypotheses. The assessment of safety and tolerability will be performed on the safety analysis set, which includes all subjects who received at least one dose of B-OT. Complete description of all statistical analyses and methods will be presented in the Statistical Analysis Plan (SAP). The SAP will be reviewed and approved by the Sponsor and will be finalized prior to database lock. Plans for PK analyses will be included in the SAP.

The sample sizes for the SAD cohorts are typical for a Phase 1 first in human (FIH) study. The total number of subjects accrued in the study will depend on the number of dose levels, but is currently set to a maximum of 24 subjects (2 cohorts with 3 subjects and 3 cohorts with 6 subjects each). The safety and tolerability of B-OT will be analyzed by appropriate descriptive statistics. All other secondary endpoints will be summarized descriptively.

The sample sizes for the MAD cohorts are typical for a Phase 1 multiple ascending dose study. The total number of subjects in the study will be 24 subjects (4 cohorts with 6 subjects each). The safety and tolerability of B-OT will be analyzed by appropriate descriptive statistics. All other secondary endpoints will be summarized descriptively.

If circumstances should arise during the study rendering the analysis inappropriate, or if in the meantime improved methods of analysis should come to light, different analyses may be performed. Any deviations from the statistical methodology defined in this protocol, reasons for such deviations and all alternative/additional statistical analyses that may be performed will be described in the CSR. Such changes to analyses may be written into an abbreviated SAP, if appropriate. The verification and review of all statistical Modelling assumptions will be documented appropriately.

All original and derived parameters as well as demographic and disposition data will be listed and described using summary statistics. All safety data (scheduled and unscheduled) will be presented in the data listings.

Demographic and baseline data will be summarised by treatment (dose level of B-OT) and overall. Pharmacokinetic data will be summarised by dose level of B-OT. Safety and tolerability data will be summarised.

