A 168-hour individual profile of plasma OT concentrations and potentially other derivate metabolites will be measured. Values will be plotted and descriptive statistics per planned sampling time point and treatment will be provided, including mean, SD, CV%, minimum, maximum, and median as well as geometric mean and its CV%.

At least the following individual PK parameters will be determined based on the concentration versus time curves in the MAD part on Day 1: AUC_τ, C_{max} , t_{max} , on Day 7: AUC_τ, $C_{max,ss}$, $t_{max,ss}$, Swing, PTF%, CL_{ss}/F , V_z/F , C_{trough} , C_{av} , C_{min} , $t_{1/2}$, AUC_{inf} and AUC_{last} as appropriate and Day7/Day1: $Ra(AUC_{\tau})$, $Ra(C_{max})$.

The lin-up log-down trapezoidal method will be used. If the logarithmic trapezoidal rule fails in an interval because non-monotonicity, then the linear trapezoidal rule will apply for that interval.

If the terminal phase is sufficiently well characterized the terminal half-life will be estimated and AUC zero to infinity (AUC_{0-∞}) will be derived from AUC_{0-last} and the extrapolated area from the last measurement point to infinity based on the terminal half-life. Within a subject, data points before time of maximal plasma concentration that are below the lower limit of quantification (LLOQ) will be replaced with zero. Within a subject, data points after time of

maximal plasma concentration that are below the LLOQ will be excluded from analysis (considered as missing). Additionally, C_{max} and t_{max} will be determined.

The individual PK parameters will be summarized, including at least number of subjects, mean, SD, CV%, median, Min, and Max, as well as geometric means and its CV%.

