## iii) After Day 7 (after steady-state)

- Terminal elimination rate constant ( $\lambda_z$ );
- Plasma elimination half-life ( $t_{1/2}$ );
- Area Under the Curve from 0 to infinity ( $AUC_{0-inf}$ );
- Area Under the Curve from 0 to the time of the last quantifiable concentration ( $AUC_{0-last}$ ).

In addition, accumulation ratios ( $Ra(AUC_{0-\tau})$  and  $Ra(C_{max})$ ) will be computed. Dose-proportionality for PK parameters of OT ( $AUC_{0-\tau}$ ,  $AUC_{last}$ , and  $C_{max,ss}$ ) will be assessed as well.

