#### 8.1.2 Computation formulas

Pharmacokinetic parameters will be calculated assuming a non-compartmental model as follows:

- $AUC_{0-t}$  (h.ng/mL) – The area under the plasma concentration versus time curve, from time 0 to the last measurable concentration, as calculated by the linear-up/log-down trapezoidal method. When concentrations are increasing (as in the absorption phase), the linear trapezoidal method will be used. When concentrations are decreasing (as in the elimination phase), the logarithmic trapezoidal method will be used. If  $C_i > C_{i-1}$  then:

$$AUC_i = AUC_{i-1} + \frac{C_i + C_{i-1}}{2} * (t_i - t_{i-1})$$

otherwise:

$$AUC_i = AUC_{i-1} + \frac{C_i - C_{i-1}}{\ln C_i - \ln C_{i-1}} * (t_i - t_{i-1})$$

where  $C_i$  is the value of observed plasma concentration at moment  $t_i$ . If the logarithmic trapezoidal rule fails in an interval due to lack of strict *monotonicity*, then the linear trapezoidal rule will apply for that interval.

- $AUC_{0-\infty}$  (h.ng/mL) The area under the plasma concentration versus time curve from time 0 to infinity, calculated as  $AUC_{0-\infty} = AUC_{0-t} + C_t/\lambda_z$ , where  $C_t$  is the last measurable concentration,  $\lambda_z$  is the terminal elimination rate constant.
- Residual area (%)  $\frac{(AUC_{0-\infty} - AUC_{0-t})}{AUC_{0-\infty}} \times 100\%$ .
- $C_{\max}$  (ng/mL) - Maximum measured plasma concentration over the time span specified.
- $t_{\max}$  (h) – Time of the maximum measured plasma concentration. If the maximum value occurs at more than one time point,  $t_{\max}$  is defined as the first time point with this value.
- $\lambda_z$  (1/h) – Apparent first-order terminal elimination rate constant calculated from a semi-log plot of the plasma concentration versus time curve. The parameter will be calculated by linear least-squares regression analysis using at least three points during the terminal log-linear phase, and “best fit” rule.
- $t_{1/2}$  (h) – Apparent first-order terminal elimination half-life will be calculated as  $t_{1/2} = \ln 2 / \lambda_z$ .
- $CL/F$  (L/h) – Apparent total body clearance following extravascular administration will be estimated as  $CL / F = \frac{Dose}{AUC_{0-\infty}}$ .
- $V_z/F$  - Apparent volume of distribution will be estimated as  $V_z / F = \frac{CL / F}{\lambda_z}$ .

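### SAP 8.2.3 computes MAD AUC0-tau by the linear trapezoid, against the protocol's lin-up/log-down rule, and leaves the lambda-z behind V/F without a planned source

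*SAP*

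**What the plan says.** **AUC rule.** Protocol 14.9 lists the SAD parameters, then the MAD parameters, and then states: "The lin-up log-down trapezoidal method will be used". It makes no exception for MAD. SAP 8.1.2 defines the SAD AUC "as calculated by the linear-up/log-down trapezoidal method" and prints the linear increment, used while concentrations rise, with a plus sign between adjacent concentrations. SAP 8.2.3(i), which covers Day 1 and steady state, defines AUC0-tau as "Area Under the Curve over a dosing interval, as calculated by the linear trapezoidal method" and prints the increment with a minus sign. SAP 8.2.3(ii) returns to the SAD rules for the remaining parameters: "After Day 7: formulae are similar to those given in" section 8.1.2. SAP section 1 says all analyses conform to protocol version 3.0, and no departure is declared.

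**Volume.** Protocol 11.2 and 14.9 list Vz/F for Day 7. SAP 2.2, 8.2.2 and 8.2.3 call it Vss/F. SAP 8.2.3 computes it as (CLss/F)/lambda-z, where lambda-z "is terminal elimination rate constant estimated from corresponding single dose". SAP 2.2 plans only AUC0-tau, Cmax and tmax on MAD Day 1. It lists lambda-z for MAD only under the heading "After Day 7 (after steady-state").

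**The concern.** An analyst who follows SAP 8.2.3 would choose the linear setting in WinNonlin for AUC0-tau. One who follows the protocol would choose lin-up/log-down. Within the SAP itself, the Day 7 profile would be integrated linearly for AUC0-tau and by lin-up/log-down for AUC0-last and AUC0-inf. The parameters affected are pre-specified MAD secondary endpoints, and the choice should not be left open until data are in hand.

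The volume definition has a similar gap. V/F is inversely proportional to lambda-z, so any error in lambda-z passes through in full. The source that the SAP names is not among the planned MAD estimates, and the planned estimate is not used.

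**Working it through.** The plan states no AUC, half-life or power figure on this point, so there is nothing of its own to reproduce. The check compares the rules on the planned sampling times.

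**Inputs**
- Times: 0, 0.25, 0.5, 0.75, 1, 1.5, 2, 4, 8, 12 and 24 h (Protocol Table 4; the 24 h sample is the Day 2 pre-dose or the Day 8 sample).
- Cmax 15.45 ng/mL, the SAD mean at 5 mg; tmax 2 h, inside the reported range of 1.67 to 2.50 h (Protocol 6.1).
- Assumed: a one-compartment oral profile C(t) = A(e^(-kt) - e^(-ka·t)), with k = ln 2 / half-life, and ka and A set to give that Cmax and tmax. Half-life 2 to 48 h. Day 7 is built by adding up seven daily doses.

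**Increment over an interval of length d, from C1 to C2**
- As printed in SAP 8.2.3: (C2 - C1)/2 × d
- Linear: (C2 + C1)/2 × d
- Log, used when concentrations fall: (C2 - C1)/ln(C2/C1) × d

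**The printed sign.** A constant 10 ng/mL over 24 h gives 0 by the printed increment. The true area is 10 × 24 = 240 h·ng/mL.

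**One interval.** With a half-life of 8 h, C(12) = 6.889 and C(24) = 2.436 ng/mL.
- Linear: (2.436 + 6.889)/2 × 12 = 55.9
- Log: (2.436 - 6.889)/ln(2.436/6.889) × 12 = 51.4

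This one sparse interval accounts for 4.5 of the 188.7 - 183.3 = 5.4 h·ng/mL gap over the whole Day 1 profile.

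**Day 1 AUC0-24 (h·ng/mL)**

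| Assumed half-life | As printed | Linear, plus sign | Lin-up/log-down | Exact | Linear vs lin-up/log-down |
|---|---|---|---|---|---|
| 2 h | -28.5 | 94.5 | 87.0 | 89.1 | +8.6% |
| 4 h | -36.4 | 130.4 | 122.6 | 123.7 | +6.3% |
| 8 h | -40.0 | 188.7 | 183.3 | 183.9 | +2.9% |
| 12 h | -36.5 | 225.7 | 222.2 | 222.6 | +1.6% |
| 24 h | -25.3 | 280.6 | 279.2 | 279.6 | +0.5% |
| 48 h | -14.4 | 318.3 | 317.9 | 318.2 | +0.1% |

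The Day 7 percentages are the same. At 8 h, for example, the Day 7 values are 217.6 and 211.4.

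**What carries over.** Cav = AUC0-tau/tau rises by the same percentage. CLss/F = Dose/AUC0-tau, PTF% (divided by Cav) and V/F (proportional to CLss/F) fall correspondingly: at most 1 - 1/1.086 = 7.9%, and 0.1% at 48 h.

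**What does not**
- Ra(AUC) is Day 7 over Day 1 in the protocol, and 8.2.3(i) applies one rule to both days. The ratio agrees between rules to within 0.0003 (at 12 h, 1.3490 against 1.3492).
- Dose proportionality on the log scale: if the profile has the same shape at every dose, both rules give a slope of 1.000. If half-life is assumed to lengthen with dose from 6 to 8 h, the slopes differ by about 0.008; from 3 to 6 h, by about 0.02.
- Cmax,ss, tmax,ss, Swing, Ctrough, Cmin, lambda-z and t1/2 do not use AUC0-tau. AUC0-last and AUC0-inf already follow 8.1.2.

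**The lambda-z source.** The words in 8.2.3 can be read two ways, and the plan supports neither.
- The SAD cohort at the same dose: these are other people (SAP 4.1 requires another 24 subjects for MAD), and only 3 of them received 1 mg.
- MAD Day 1: a single dose in the same subject, but lambda-z is not a planned Day 1 parameter and sampling of that dose stops at 24 h.

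The planned post-Day 7 lambda-z has samples to 168 h after the last dose.

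**The label.** SAP 8.1.2 itself defines (CL/F)/lambda-z as Vz/F. The same quotient in 8.2.3 is called Vss/F.

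**The case against.** The minus sign is unlikely to reach any result. The text was machine-read, so the sign needs checking against the PDF. The sentence beside it names the linear trapezoidal method, 8.1.2 prints that rule correctly, and WinNonlin computes the parameters. This stands: a reader might infer that negative AUCs would be reported, and the documents do not support that.

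A reader might also infer that one wrong line corrupts most MAD secondary endpoints, or that SAD and MAD AUCs could not be compared. Neither holds. Many MAD parameters do not use AUC0-tau, Ra(AUC) is unchanged, the slope barely moves, no SAD-versus-MAD AUC comparison is planned, and a gap of at most about 9% would not prevent one. The protocol adds in 14.1: "The study is exploratory and is not powered to address any pre-defined hypotheses".

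On volume, it would be too strong to say that no MAD subject has a lambda-z. Each has one planned after Day 7. A Day 1 estimate from samples at 4, 8, 12 and 24 h is also possible, and SAP 8.2.4 uses the term single dose for what the protocol defines as Day 1. A several-fold error in V/F could be produced by assuming a slow second phase of decline, but the documents give neither a half-life nor a second phase.

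What survives is the undeclared conflict over the AUC rule and the wrong label and unplanned lambda-z source for V/F.

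**Conclusion.** Wrong as written; should be fixed. SAP 8.2.3 contradicts Protocol 14.9 on the integration rule and applies a different rule from the one that 8.2.3(ii) takes from 8.1.2. The size is modest: AUC0-tau about 0.1% to 8.6% higher than under the protocol's rule, with matching shifts in CLss/F, Cav, PTF% and V/F. That range rests on an assumed one-compartment profile and assumed half-lives of 48 h down to 2 h; the shorter the half-life, the larger the gap. The statement about Ra(AUC) assumes that its denominator is MAD Day 1, as the protocol says.

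The V/F defect stands on the text alone. The quotient is the protocol's Vz/F, and its lambda-z should be the planned post-Day 7 estimate. Its numerical effect cannot be stated from the documents.

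**What to change.** In SAP 8.2.3:
- For AUC0-tau on Day 1 and Day 7, state linear-up/log-down as in 8.1.2, and correct the sign of the printed increment after checking the PDF.
- Rename Vss/F to Vz/F, here and in 2.2 and 8.2.2. Compute it as (CLss/F)/lambda-z with each MAD subject's own post-Day 7 lambda-z.
- Apply the 8.1.1 reliability rules to that lambda-z (at least 3 terminal points excluding Cmax, adjusted R-squared at least 0.80). Otherwise report V/F as not calculated; 8.2.2 at present says this only for AUC0-inf and t1/2.

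Leave the linear interpolation of single missing concentrations in SAP 5.9.1(iv) as it is. Protocol 14.4 specifies the same, so changing it would open a new conflict.

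The cost is SAP wording before database lock. No protocol amendment, extra sample or new software is needed.

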## 8.2.4 Accumulation ratios

Two accumulation ratios will be computed:

- $Ra(AUC) = \frac{AUC_{\tau}}{AUC_{0-\tau}}$ ,  $AUC_{0-\tau}$  is AUC for single dose on the dosing interval;
- $Ra(C_{\max}) = \frac{C_{\max,ss}}{C_{\max}}$ ,  $C_{\max}$  is maximal concentration for single dose.

## 8.2.5 Dose proportionality (MAD)

On Day 7, dose-proportionality for PK parameters of OT and B-OT ( $AUC_{0-\tau}$ , and  $C_{\max,ss}$ ) will be assessed by the power model [6]. The slope and the associated 90% CI will be reported. The same approach will be applied as for SAD ([sec.8.1.3](#)).

## **9. EVALUATION OF EFFICACY PARAMETERS**

Not applicable.

## 10. EVALUATION OF PHARMACODYNAMIC PARAMETERS

The exploratory endpoints of the study are to evaluate the pharmacodynamics (PD) by measuring the transketolase activity in erythrocytes (SAD part of the study) or white blood cells (MAD part of the study).

All pharmacodynamic results will be presented and explored according to the dose administered after the end of SAD and MAD parts of the study. If PD results are available at the end of the SAD and MAD part of the study, these will be listed where applicable.

### 10.1 SAD part

Descriptive statistics (n, arithmetic mean, standard deviation [SD], maximum, median, and minimum) will be reported for each time point. Individual and mean concentration time data will also be plotted.

LoQ and missing concentrations will be treated as is stated in [section 5.9.1](#).

Blood samples will be taken according to the schedule given in [Table 1](#).

**Table 1. PK/PD SAMPLING TIMEPOINTS: SAD Part**

| PK sample timepoint (hr.)       | Allowed time deviation | PD sample timepoint (hr.)       | Allowed time deviation |
|---------------------------------|------------------------|---------------------------------|------------------------|
| Pre-dose (35 min before dosing) | +/- 5 min              | Pre-dose (35 min before dosing) | +/- 5 min              |
| 0.25                            | +/- 5 min              | -                               | -                      |
| 0.5                             | +/- 5 min              | -                               | -                      |
| 0.75                            | +/- 5 min              | -                               | -                      |
| 1.0                             | +/- 5 min              | 1.0                             | +/- 5 min              |
| 1.5                             | +/- 5 min              | -                               | -                      |
| 2                               | +/- 5 min              | 2.0                             | +/- 5 min              |
| 4                               | +/- 10 min             | 4.0                             | +/- 10 min             |
| 8                               | +/-15 min              | 8.0                             | +/-15 min              |
| 12                              | +/- 30 min             | 12                              | +/- 30 min             |
| 24                              | +/- 1 hr               | 24                              | +/- 1hr                |
| 36                              | +/- 1 hr               | -                               | -                      |
| 48                              | +/- 1hr                | 48                              | +/- 1hr                |
| 72                              | +/- 1hr                | 72                              | +/- 1hr                |
| 168                             | +/- 2 hr               | 168                             | +/- 2 hr               |

### 10.2 MAD part

Descriptive statistics (n, arithmetic mean, standard deviation [SD], maximum, median, and minimum) will be reported for each time point. Individual and mean concentration time data will also be plotted.

LoQ and missing concentrations will be treated as is stated in [section 5.9.1](#).

Blood samples will be taken according to the schedule given in [Table 2](#).

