**2.3 Exploratory Objectives**

Exploratory objective is to evaluate the pharmacodynamics (PD) by measuring the transketolase activity in erythrocytes in the SAD part of the study and in white blood cells in the MAD part of the study.

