### 5.9.1 Pharmacokinetic data

Concentrations below the Lower Limit of Quantification (LLoQ) will be indicated as Below the Limit of Quantification (BLoQ) on individual results tabulations. For all descriptive statistics, pre-dose BLoQ concentrations will be set to zero (for single dose concentrations). All other BLoQ concentrations will be set to LLoQ/2.

For computation of PK parameters and relevant statistical evaluations:

- i) Zero (0) imputation will be implemented before the first quantifiable concentration;
- ii) LLoQ/2 imputation will be used between quantifiable concentrations, and
- iii) Values will be ignored (i.e. considered as missing) after the last quantifiable concentration.
- iv) Values reported as missing (no sample or no valid analytical result) will be set as such and will not be included in PK and statistical evaluation. If single data points for plasma B-OT or OT concentrations are missing, the AUC parameters will be derived by linear interpolation with regard to the two neighboring non-missing concentrations.
- v) If the actual sampling time is missing, but a valid concentration value has been measured, the scheduled protocol time will be used for the calculation of derived PK. Pre-dose sampling time will be considered as if it had been taken simultaneously with the drug administration (at zero-hour time point).

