### 6.2 Demographics and baseline measurements

Baseline is defined as the last value prior to dosing. Absolute change from baseline will be calculated for all continuous safety parameters. Baseline demographic data will be tabulated and presented by dose.

Demographic data: age, height, weight and body mass index (BMI) will be summarized by descriptive statistics (n, mean, standard deviation, median, minimum and maximum), and gender and race, will be summarized by the number and percentage of subjects in each category in Table “*Demographics*”.

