##### Pharmacodynamics

Table II.14.2.4 Pharmacodynamic Tests: Summary of (ng/mL) versus Nominal Sampling Time

Table II.14.2.5 Summary of Pharmacodynamic Parameters

Figure II.14.2.3 Arithmetic means concentration-time plot per treatment

Figure II.14.2.4 Geometric means concentration-time plot per treatment

Figure II.14.2.5 Individual concentration-time profiles - PD

Figure II.14.2.6 Overlaying individual concentration-time profiles – PD

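### Transketolase activity is summarised per time point only; no change from the subject's own pre-dose value and no PD parameter is defined, and the borrowed PK BLQ rules do not suit an enzyme activity

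*SAP*

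**What the plan says.** - **PD summaries.** SAP 10.2 (MAD) states "Descriptive statistics (n, arithmetic mean, standard deviation [SD], maximum, median, and minimum) will be reported for each time point" and "Individual and mean concentration time data will also be plotted". SAP 10.1 (SAD) uses the same wording. Protocol 14.9 covers PK and PD in its title but contains no PD method.
- **Use of baseline.** SAP 6.2 says "Absolute change from baseline will be calculated for all continuous safety parameters", and protocol 14.7 has the same restriction to safety parameters. In the SAP output list, the hematology, biochemistry and vital-sign tables include change from baseline; the PD tables do not.
- **PD parameters.** Tables I.14.2.5 and II.14.2.5 and Listings I.16.2.6.2 and II.16.2.6.2 are to show PD parameters. None is defined in either document.
- **BLQ handling.** Both PD sections refer to the PK rules: "LoQ and missing concentrations will be treated as is stated in" SAP 5.9.1. For descriptive statistics, that section says "pre-dose BLoQ concentrations will be set to zero (for single dose concentrations") and then "All other BLoQ concentrations will be set to LLoQ/2". For PK parameters and related evaluations, it sets zero before the first quantifiable value, LLoQ/2 between quantifiable values, and missing after the last.
- **Matrix and units.** SAP 2.3 specifies "transketolase activity in erythrocytes in the SAD part of the study and in white blood cells in the MAD part". The output tables are titled "Pharmacodynamic Tests: Summary of (ng/mL) versus Nominal Sampling Time".

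**The concern.** Oxythiamine is described in protocol 6.1 as an inhibitor of transketolase, so the PD question is how far each subject's activity falls from where it started. A mean per time point does not answer that. It carries the full spread of enzyme levels between subjects, and its SD says nothing about the spread of the response.

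SAP section 10 says PD results will be explored according to dose, but each dose is given to a different small cohort and there is no control. A cohort that happens to have low or high enzyme levels at baseline can look like a dose effect or hide one. The PD analysis set (SAP 4.3.3) asks for at least one post-dose value and no pre-dose value, so pre-dose and post-dose means need not even come from the same subjects.

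Transketolase activity is the only PD measure in the study, so what is at stake is whether its evidence on target engagement can be read.

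The BLQ reference adds a smaller problem. Zero is a natural value for a drug before the first dose; it is not one for an enzyme that the body makes.

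**Working it through.** **Inputs from the documents.** SAD cohorts have 3, 3, 6, 6 and 6 subjects; MAD cohorts have 6 each (protocol 8.1.2). PD samples per subject: SAD 10 (pre-dose, 1, 2, 4, 8, 12, 24, 48, 72, 168 h); MAD 6+1+6+1+6+1 = 21. Both counts agree with protocol Table 5, and both schedules start with a Day 1 pre-dose sample. The documents give no SD, CV, correlation or LLoQ for transketolase activity, so there is no planned figure to reproduce.

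**Assumptions.** Between-subject CV 25% of the pre-dose mean, equal before and after dosing (range 20% to 30%); within-subject correlation ρ = 0.5, 0.8 or 0.9. Half-widths are in percentage points of the pre-dose mean.

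**Step 1: pre-to-post difference in one cohort.** A reader with only the two time-point means and SDs has

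SE(unpaired) = CV × √(2/n) = 25 × √(2/6) = 14.4; half-width = t(0.975, 10) × 14.4 = 2.228 × 14.4 = 32.2.

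With each subject's own pre-dose value,

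SE(paired) = CV × √(2(1−ρ)/n), which is √(1−ρ) times the unpaired SE; half-width = t(0.975, 5) × SE, with t = 2.571.

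| n = 6 | SE ratio | CV 20% | CV 25% | CV 30% |
|---|---|---|---|---|
| unpaired | 1 | 25.7 | 32.2 | 38.6 |
| paired, ρ = 0.5 | 0.71 | 21.0 | 26.2 | 31.5 |
| paired, ρ = 0.8 | 0.45 | 13.3 | 16.6 | 19.9 |
| paired, ρ = 0.9 | 0.32 | 9.4 | 11.7 | 14.1 |

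For the two SAD cohorts of 3 at CV 25%, the unpaired half-width is 56.7; paired, it is 62.1, 39.3 and 27.8. At ρ = 0.5 the paired interval is wider although its SE is smaller, because t has 2 rather than 4 degrees of freedom.

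**Step 2: comparison between doses.** With no drug effect, the means of two cohorts of 6 differ by chance with SD 25 × √(2/6) = 14.4 points. Per-time-point means carry that difference straight into the dose comparison.

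**Step 3: the BLQ rules, with LLoQ set to 1 for illustration.**

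- *Pre-dose zero.* All subjects at 0.8 before and after a single dose, so no true change. The descriptive rule reports 0 and then 0.5: a false rise. Percent of baseline is undefined.
- *Dropping trailing BLQ.* Pre-dose values 2, 2.5, 3, 1.8, 2.2, 2.8 (mean 2.383) with true inhibition 60%. Three of six post-dose values stay quantifiable (1.0, 1.2, 1.12; mean 1.107). Against the pre-dose mean of all six, inhibition reads 1 − 1.107/2.383 = 54%. At true inhibition 70%, no post-dose value remains.
- *LLoQ/2 after dosing.* In the same six subjects, true inhibition of 50%, 60%, 70% and 80% reads as 53%, 66%, 79% and 79%. Here the rule overstates the effect until true activity falls below LLoQ/2.

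**The case against.** PD is exploratory, and protocol 12.4.4 makes the validated MAD assay conditional on availability. The pre-dose sample is a scheduled time point, so it is tabulated, plotted in each individual profile and listed. LLoQ/2 already governs every BLQ value in the descriptive statistics except a single-dose pre-dose one. All of this stands, and it rules out three stronger readings that a reader might reach:

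- *That the pre-dose value is ignored.* It is shown; what is missing is any variable derived from it.
- *That the BLQ rules always work against an inhibition signal.* The pre-dose zero and the dropping of trailing values can. LLoQ/2 can inflate inhibition, as step 3 shows. The zero is limited to single-dose concentrations, so in the MAD it reaches Day 1 pre-dose at most. The trailing rule is written for PK parameters and related evaluations, and reaches PD only if PD parameters are derived under it.
- *That the change from erythrocytes to white cells calls for separate reporting of SAD and MAD.* SAP section 5 and the two output lists already keep the parts apart.

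It is also fair to say that change from one noisy baseline does not remove baseline imbalance perfectly when ρ is below 1, and that the choice between absolute and percent change is partly preference. Neither is a reason to define no baseline-adjusted variable at all.

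**Conclusion.** The point holds as a gap in the PD analysis, not as an error in a primary or secondary result. The text settles the main part: no baseline-adjusted PD variable exists, the PD-parameter tables are empty titles, and the sample needed to fill them is already scheduled. The gain in precision depends on the assumed CV and correlation. At n = 6 and CV 25%, the half-width goes from about 32 points to 26, 17 or 12; in the cohorts of 3, a gain in interval width needs a correlation above 0.5.

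The BLQ part is a mismatch of rule and endpoint whose practical effect cannot be sized, since the documents give no LLoQ for activity and do not show whether any value would fall below it. The ng/mL unit in the PD table titles is a labelling slip.

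**What to change.** In SAP section 10, with matching changes to the output list:

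1. Define the PD baseline as the subject's Day 1 pre-dose activity.
2. Derive change and percent change from it for each subject. Summarise and plot both by dose and time beside the planned raw values, using subjects with both values.
3. Define the PD parameters for the existing tables and listings, for example maximum inhibition and, in the MAD, inhibition at Day 7 pre-dose.
4. Replace the reference to 5.9.1 with one PD-specific BLQ rule, identical before and after dosing, that neither sets values to zero nor discards them. Report the number of BLQ values by dose and time. LLoQ/2 would meet this, with the caveat that it can overstate inhibition, so the counts must be read with it.
5. Replace ng/mL in the PD table titles with the assay's activity units.

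The cost is SAP wording and simple derived variables. No sample, visit or assay is added.
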